5.0 Inclusion and Exclusion Criteria/ Study Population

Only women 18-45 years who are lactating and their preterm infants (<35 weeks) within the first week postpartum will be eligible for the study. Men will be excluded on the basis of the study criterion of lactation. Infants of both genders will be followed along with their mothers. Women who deliver at MUSC will be eligible for participation.

- a. **Inclusion Criteria for Lactating Women:** Women with documentation of fully breastfeeding who present within one month of delivery, who are 18-45 years old and in good general health will be eligible for participation.
- b. **Exclusion Criteria for Lactating Women:** Women with preexisting type I or type II diabetes, hypertension requiring medication or parathyroid disease will not be eligible for participation in the study. Those women with active thyroid disease will not be eligible for inclusion in the study; however, women who have normal thyroid parameters on thyroid replacement hormone will be eligible for participation in the study. In addition, because of

the potentially confounding effect of multiple gestations/births (e.g. twins, triplets), women with multiple gestations/births will not be eligible for participation in the study.

No racial or ethnic groups will be excluded from this study.

6.0 Number of Subjects

For this initial Pilot study, we will enroll 50 mothers/infant dyads in total, 25 in the control and 25 in the placebo group.

7.0 Setting

Mothers and their infants will be initially seen in the MUSC Shawn Jenkins Children's Hospital NICU. If still inpatient for the remainder of their 2-3 visits, they will continue to be seen there. Following discharge, study visits will either be conducted in infant High-Risk Clinic or the Research Nexus clinic (MUSC Clinical Sciences Building, suite 214). The infant High-Risk Clinic has exam rooms, registration personnel and nursing staff. The NEXUS outpatient clinic has exam rooms, nursing staff, registration staff and lab personnel. We will meet the subjects at any of these sites and conduct the visits. There is only potential for 3 outpatient visits.

[figure not shown]
8.0 Recruitment Methods

Mothers of infants and their infants who both meet entry criteria will be approached by someone directly involved in the infant's care which could potentially also be a study personnel. The mother will then be consented by the study personnel within the first week of their infants' NICU stay. This could be by telephone if mom has been discharged or in person. Chart review will be used to determine eligibility.

9.0 Consent Process

Before performing any procedure, informed consent will be obtained from the mother enrolled in this study for both her and her infant child. This consent will be obtained by the PI, co-investigators, or the Study Coordinator. Consent will be given following an informative discussion period and then either by reading the Informed Consent Agreement to the subject or by allowing the subject to read the consent, then reviewing it with the subject. This will take place at MUSC, either in the NICU or on Labor and Delivery. There could potentially be no waiting period between informing the prospective subject and obtaining the consent.

10.0 Study Design / Methods

Mother

1. Visits: Each mother accompanied by her breastfeeding infant will be instructed to either present to the infant's room in the NICU, Infant High-Risk Clinic, or NEXUS clinic for evaluation.

2. Sociodemographic and Medical History: Following a woman's informed consent, each woman will have generated a study record that will include identifying information such as name, address, sociodemographic, ethnic and racial background, and medical information that will include past medical history and history about the most recent pregnancy, delivery, and postpartum state. This information will be collected from the mother via interview and from her clinical medical record and will be collected for research purposes only.

3. Questionnaires: Each woman will be asked to complete a series of questionnaires throughout the study that pertain to her health status, activity level, clothing use, dietary intake, and labor/delivery and breastfeeding history.

Initial Visit	1 Month Follow Up	2 Month Follow Up	3 Month Follow Up
Sociodemographic (Q1)			
Pregnancy & Delivery (Q2)			
Newborn History (Q3)			
Physical Activity (Q4)	Physical Activity (Q4)	Physical Activity (Q4)	Physical Activity (Q4)
Maternal Clothing (Q5)	Maternal Clothing (Q5)	Maternal Clothing (Q5)	Maternal Clothing (Q5)
Breast Feeding Log (Q6)			
	Breastfeeding Review (Q7)	Breastfeeding Review (Q7)	Breastfeeding Review (Q7)
	Infant Health/Diet (Q8)	Infant Health/Diet (Q8)	Infant Health/Diet (Q8)
Maternal/Infant Health Assessment (Q9)			
Edinburgh PPD Screen (Q10)			
Online DHQ-III	Online DHQ-III	Online DHQ-III	Online DHQ-III

4. Body Mass Index (BMI): Based on a woman's weight and her height, a woman's body mass index (BMI) will be calculated at her initial visit and all subsequent visits, and will be recorded in Redcap

5. Daily Vitamin D and Prenatal Vitamins: Using a web-based computer program, each mother will be randomized to receive one of two vitamin D₃ regimens (600 or 6,600 IU/day). The 600 IU of vitamin D group will receive this from their prenatal vitamin. The experimental group will continue their prenatal vitamin (600IU vitamin D), and 6,000 IU vitamin D which will be from taking six, 1,000IU Vitamin D gummies.

6. Laboratory Data from Blood and Urine Samples: At initiation of the study and at each monthly visit (1, 2, and 3), each woman will have blood sample drawn (20 mL) for detailed analysis of vitamin D and calcium homeostasis. The total blood to be drawn from woman during the 3-month study period will be 60mL (<1/2 cup). In addition, she will be asked to provide a urine sample to measure her urinary calcium/creatinine. A total of up to 4 blood and urine samples will be obtained from each mother, depending on continued participation in the study.

7. Milk Samples: At time of initiation of the study and at each monthly visit (1, 2, and 3), each mother will provide a milk sample from her left breast. The skin will be washed with warm water prior to pumping. The amount obtained will be less than 20 mL at each visit. This milk can be pumped that day and kept refrigerated or pumped at time of visit. This will then be run on the Calais Milk Analyzer to be tested for Fat, Total Protein, True Protein, Lactose, and Calorie/ounce.

8. Degree of Skin Pigmentation will be measured at each visit using the Smart Probe 400, a commercially available spectrometer, which is placed lightly on the skin. Sites to be measured include the inner and outer lower arm and the buttocks.

9. Depression/Anxiety Screening: Each mother enrolled in the study will complete the Edinburgh Postnatal Depression Scale (EPDS) at each monthly study visit. Women who score above the threshold consistent with possible depression will be referred to the appropriate trained professional. Any woman who responds “yes” to the suicide related statements in the EPDS will be immediately referred to the Emergency Room for further evaluation and treatment.

Infant

1. Outpatient Visits: Each mother will be asked to bring her infant as a scheduled outpatient at her monthly visits. If still admitted to the NICU, these monthly visits will be held in the MUSC NICU. If discharged, visits will be held at Infant High-Risk Clinic or NEXUS clinic. These visits will be the initial at approximately 3-7 days of life, then at months 1, 2, and 3.

2. Questionnaires: We will ask each mother to complete a questionnaire about her baby’s dietary type (breastfeeding, formula-supplementation), and feeding frequency for the week prior to each outpatient visit. Each questionnaire will take approximately 5 minutes to complete. See maternal section table.

3. Daily Vitamin D Supplementation: Infants of mothers who receive 600 IU of vitamin D₃ will receive 400 IU of vitamin D₃ in the form of drops. Infants of mothers who receive 6600 IU of vitamin D₃ will receive placebo drops.

3. General Health Assessment of Infant: At 1 week after delivery and then monthly until 3-months of age, each enrolled infant will undergo a growth (measuring head circumference, weight, length, head circumference, Ponderal index, body mass index [BMI]) and general health assessment.

4. PEAPOD Assessment: Prior to discharge from the NICU, the infant will also be placed in the PEAPOD® for body mass composition analysis. The material and data will be specifically obtained for research purposes. There is minimal risk. This is a safe device in which the infant lays in for 2 minutes.

5. Blood Sample from Infant: At initial visit, 1-, 2- and 3-months of age, each infant will have a blood sample 4mL (<1tsp) taken from either a vein (infant’s hand, arm or foot) or the heel. Total amount obtained will be less than 12mL (<1 1/2 tablespoon). The serum sample will be analyzed for vitamin D and calcium concentration. Parents will be counseled that if their infant is vitamin D deficient, the infant’s primary care physician and they will be contacted regarding the finding(s) with recommended follow-up.

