14.0 Withdrawal of Subjects

- Describe anticipated circumstances under which subjects will be withdrawn from the research without their consent, including stopping participation for safety reasons.
 - Mother and infant move away from the study site
 - Infant is transferred to another facility
 - If mother had baseline hypercalcemia or hypercalciuria or baby had hypercalcemia, they would exit the study
- Describe any procedures for orderly termination of subjects by investigator.
 - The PI would notify the subjects in both writing and verbally if their participation is terminated.
- Describe procedures that will be followed when subjects voluntarily withdraw from the research, including partial withdrawal from procedures with continued data collection.
 - For voluntary withdrawal, the participant would notify the PI in writing. If mother requests to withdrawal either her or the infant, they will both be removed from the study without further data collection.

15 Risks to Subjects

1. The Risks of Phlebotomy:

- a. **Maternal:** The total amount of blood to be drawn at each maternal visit is 15 mL. Using aseptic technique, blood will be drawn monthly for a maximum of 4 blood draws (initial visit and monthly beginning at month 1 through month 3) during the study period and the total amount of blood over the study period will not exceed 60mL (<½ cup). Momentary discomfort may occur when skilled technicians or nurses perform phlebotomy with slight pain when the needle is inserted into a vein. Pressure will be applied to the arm following the procedure to minimize the risk of bruising; however, despite these efforts, a bruise may form at the site. Lastly, there is a slight chance of inflammation of the vein and/or blood clot formation, but this is extremely rare.

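### Maternal blood per visit is 20 mL in Section 10 but 15 mL in Section 15; four draws at 20 mL make 80 mL, above the 60 mL that both sections state.

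*Protocol*

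**What the plan says.** Two places in the protocol give the maternal blood volume.

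- **Section 10.0, Study Design / Methods, Mother, item 6.** At study start and at each of the three monthly visits, "each woman will have blood sample drawn (20 mL) for detailed analysis of vitamin D and calcium homeostasis". The same item puts the study total at 60 mL ("The total blood to be drawn from woman during the 3-month study period will be 60mL") and confirms the number of draws: "A total of up to 4 blood and urine samples will be obtained from each mother, depending on continued participation in the study".
- **Section 15, Risks to Subjects, item 1a (Maternal).** Here the volume is different: "The total amount of blood to be drawn at each maternal visit is 15 mL". The number of draws is the same, at most four, at the initial visit and months 1 to 3. The total is worded as a ceiling: "the total amount of blood over the study period will not exceed 60mL".

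Section 4.0 (Study Endpoints) makes the mother's 25(OH)D at 3 months a primary outcome and lists her serum calcium at months 1, 2 and 3 among the safety endpoints. The fourth draw therefore serves both.

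**The concern.** Section 10 is the procedural section, which site staff would follow when drawing blood. Section 15 is the risk statement, which describes the burden on the mother. They give different volumes for the same visits, and the Section 10 volume is not compatible with the total in its own item. A mother who attends all four visits under Section 10 would give more blood than Section 15 says she will. At stake is whether the procedure stays within a participant maximum that the protocol itself sets, and whether any participant information built on these sections is accurate. The sample size, the randomization and the analysis are not affected.

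**Working it through.** **Inputs**

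| Quantity | Section 10.0, Mother, item 6 | Section 15, item 1a |
|---|---|---|
| Volume per draw | 20 mL | 15 mL |
| Scheduled draws | 4 (initial, months 1, 2, 3) | 4 at most (initial, months 1, 2, 3) |
| Stated total | 60 mL, as a plain total | 60 mL, as a maximum |

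**Formula:** total = volume per draw × number of draws.

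**Step 1. Reproduce each stated total from its own section.**

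- Section 10: 20 × 4 = 80 mL. The stated 60 mL is not reproduced.
- Section 15: 15 × 4 = 60 mL. The stated 60 mL is reproduced.

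**Step 2. Look for a reading that gives Section 10's 60 mL.**

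- 20 × 3 = 60 mL, but this leaves out one of the four scheduled visits.
- 15 × 4 = 60 mL, but this uses the volume from Section 15.

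Neither uses the figures in Section 10 as they stand.

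**Step 3. Cumulative volume for a mother who completes the study.**

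| After draw at | 20 mL per draw | 15 mL per draw |
|---|---|---|
| Initial visit | 20 mL | 15 mL |
| Month 1 | 40 mL | 30 mL |
| Month 2 | 60 mL | 45 mL |
| Month 3 | 80 mL | 60 mL |

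**Step 4. Size of the excess at 20 mL per draw.** 80 − 60 = 20 mL, and 20 / 60 = 33% of the maximum. The 60 mL is reached exactly at month 2, so the month-3 draw is the one that goes over. At 15 mL per draw, all four draws fit with nothing to spare.

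**The case against.** Four arguments can be made against the point.

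1. **The number of samples is worded as up to four, depending on continued participation.** A mother who leaves after three draws of 20 mL would give 60 mL. But a total and a maximum have to hold for a mother who completes the study, and she has four draws. This does not remove the conflict.
2. **The 20 mL might have strayed in from the milk sample.** Milk has its own entry, item 7 of the same section, with its own volume of less than 20 mL. Item 6 attaches its 20 mL to the blood draw. A drafting slip is possible, but the text as it stands is an instruction about blood.
3. **The lay description still holds.** Both sections describe the total as less than half a cup. Taking half a US cup as about 118 mL (a unit conversion that is not in the documents), 60 mL and 80 mL both fit. That is true, but it does not make the millilitre figures agree.
4. **The practical size is modest.** The excess is 20 mL over three months in adult women, and nothing in the documents suggests that it is harmful. This stands, and it is why the point is minor.

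A reader might also infer two stronger things, and the documents support neither. The first is that the two sections state different totals. They do not: both say 60 mL. The second is that the limit will cost the trial its month-3 maternal sample, and with it a primary outcome. Both sections schedule that draw, and Section 15 counts it within its maximum of four: "blood will be drawn monthly for a maximum of 4 blood draws (initial visit and monthly beginning at month 1 through month 3". No rule tells staff to omit a sample once 60 mL has been reached. The protocol gives no assay volume either, so it does not show that either per-visit figure would endanger the measurement.

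**Conclusion.** The inconsistency is real and can be verified from the protocol alone. The per-visit volume conflicts between sections (20 mL against 15 mL), and Section 10's 20 mL at four visits does not give its own 60 mL. Following Section 10 through month 3 would take 80 mL, which is 20 mL or 33% above the Section 15 maximum.

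This rests on two conditions: that the mother completes all four draws, and that the 20 mL figure is the one followed. The word maximum comes from Section 15 only; Section 10 gives 60 mL as a plain total. That Section 15 is consistent with itself does not prove that its volume is the intended one. Loss of primary-outcome data is not shown. Severity is minor: an operative figure needs correcting, with no consequence for the statistical design.

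**What to change.** Reconcile Section 10.0 (Mother, item 6) with Section 15 (item 1a). State one per-visit maternal blood volume in both places, and make that volume times the four scheduled draws equal to the stated total and to the stated maximum, so that the month-3 draw lies within it. The sponsor has to decide whether the per-visit figure or the total is the one to change. Any participant information that repeats these figures should be brought into line at the same time. The cost is a wording correction in an amendment, with no change to the visit schedule, the sample size or the analysis.

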1.0 Objectives / Specific Aims

The overall goal of this study is to assess maternal vitamin D status along with diet, and milk composition to, in turn, evaluate if infant vitamin D status can be improved with increased maternal supplementation and diet education. Our **central hypothesis** is that by maximizing maternal vitamin D status, there will be an increase infant 25(OH)D concentration in breastfed, preterm infants. This hypothesis will be tested by performing the following Specific Aims.

Aim 1: Determine the efficacy, effectiveness, and safety of maternal and premature infant vitamin D supplementation as a function of maternal vitamin D status, lactation status, and ethnicity.

H₁: Maternal supplementation of high dose (6,600 IU) vitamin D₃/day will be safe for lactating mothers.

H₂: It is anticipated that only high dose (6,600 IU) vitamin D₃/day supplementation of lactating mothers will provide sufficient antirachitic activity in breast milk to prevent vitamin D deficiency in nursing premature infants, regardless of ethnicity/race.

H₃: High-dose maternal supplementation will be safe and more effective than infant vitamin D supplementation alone, without any adverse side effects or health consequences in the mother or infant.

Consented lactating women who delivered preterm infants <35 weeks' gestation admitted to the MUSC NICU will be randomized 3-7 days following delivery to either 1 of 2 study groups: Group A (standard therapy of 600 IU vitamin D₃/day), Group B (high dose supplementation of 6,600 IU Vitamin D₃/day). As such, infants whose lactating mothers are randomized to the 600-IU/day group will receive 400-IU/day oral vitamin D₃ (recommended practice). Those infants of lactating mothers assigned to Group B will receive placebo. Calcium homeostasis will be monitored in all groups. Safety will be assessed throughout the study on a case-rather than a treatment arm basis using cautionary levels as the stop rule with intervention prior to exceeding normal urinary calcium/creatinine ratios in mothers and serum calcium concentrations in both mothers and infants. Through these proposed studies, the prevalence of vitamin D deficiency among mothers and their infants, and the utility of maternal therapeutic intervention with vitamin D₃ will be assessed.

Aim 2: Aim 2: Evaluate and maximize maternal milk composition.

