2.0 Background

Human milk remains the favorable form of nutrition for the neonate and infant (1). Neonatal vitamin D stores are inversely related to gestational age (2). Along with this, two-thirds of fetal calcium is accumulated in the third trimester. Postnatal risk factors for vitamin D deficiency (VDD) of preterm neonates include decreased sunlight exposure, difficulties with adequate enteral nutrition, and higher requirements for vitamin D. All these factors along with use of diuretics and steroids, lead to an increased risk. Many studies have shown the importance of vitamin D in neonatal and infant health. Munshi et al. found that 80% of ELBW and VLBW infants at Albany Medical Center were deficient or insufficient in vitamin D at 1 month of age (3). Along with deficiency, the incidence of metabolic bone disease is still elevated at 32% of VLBW and 54% of ELBW (4, 5). There is also a significant association between respiratory distress syndrome (RDS) and vitamin D deficiency, especially in infants \leq 30 weeks(6).

Maternal breast milk is the recommended source of nutrition for both full and preterm infants; however, if mother is deficient in vitamin D, her milk provides limited vitamin D, with roughly 3-4 IU/kg/day provided (7, 8). It has also been found that mothers and their preterm infants were more likely to be vitamin D deficient than mothers and their infants who carried to term. To further worsen this, those preterm infants who are not fed mother's own milk (MoM) are given donor breast milk. Unfortunately, through pasteurization there is 10-20% less vitamin D (9).

Maternal vitamin D status as measured by total circulating 25(OH)D concentration is influenced by many factors including ethnicity, season, high BMI, gestational diabetes, socioeconomic status (poor diet), and prenatal intake (10). From an ethnicity standpoint, African American, Middle Eastern, and Asian women are at highest risk for vitamin D deficiency. To no surprise, these are also the populations at increased risk of preterm delivery. In South Carolina in 2010, our group showed that vitamin D deficiency [defined as 25(OH)D <20 ng/mL (50 nmol/L)] was around 48% overall, with 68.3% of African-American women being deficient (11). In our NICHD vitamin D supplementation trial, there were similar findings with significant deficiency in African American and Hispanic women at baseline (12).

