4. **The Risk of Maternal Vitamin D Supplementation on the Infant:** The developing infant's vitamin D levels are 50% of maternal serum levels at birth and rise gradually over the next 2-3 months if there is adequate delivery or synthesis (by skin). Because mothers who are breastfeeding and who are deficient in vitamin D produce milk that is deficient in vitamin D, there is a need to supplement either the infant directly or the mother herself. This study is designed to increase maternal circulating 25(OH)D levels of lactating women through the use of high dose supplementation. Approximately ~20% of maternal vitamin D passes into the milk, and therefore, the risk of hypervitaminosis D in infants whose mothers are receiving the 6,600 IU/day vitamin D₃ regimen—based on predicted maternal circulating 25(OH)D is extremely low (22). There is a risk of hypovitaminosis D to the infant whose mother is receiving the 600 IU/day D₃ regimen if that infant is not receiving the infant vitamin D₃ drops that are prescribed as part of that treatment arm (Group A).

Minimizing Risk of Hypovitaminosis D Identified by an Infant's Participation in this Study:

As an additional safety measure, if at visit 4, any infant in any treatment arm, circulating 25(OH)D concentration is found to be below normal [defined *a priori* as <20 ng/mL (<50 nmol/L)], will be supplemented with the 400 IU vitamin D/day. If an infant's circulating 25(OH)D concentration is <10 ng/mL (<25 nmol/L) and is associated with a serum calcium level of <7.5 mg/dL (<18.75 nmol/L) at 3 months or older, then compliance of mother with her prescribed vitamin D regimen and that of the infant will be assessed. If mother has been compliant with the prescribed infant vitamin D₃ supplementation and the infant continues to have evidence of vitamin D deficiency with hypocalcemia, the infant will be referred to their pediatrician for further evaluation.

5. **The Risk of Milk Collection:** There is minimal physical risk in donating a milk sample either by using a manual or electric pump.
6. **The Risk of Breach of Confidentiality through Collection of Medical History and Clinical Laboratory Data:** As with any research study, there is a small risk that medical information, laboratory reports and data could become available to individuals outside of the study. All study personnel will adhere to HIPAA guidelines and regulations.

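### Before the month-3 rescue, no rule changes a Group B infant's placebo drops when mother's own milk, the infant's only study source of vitamin D, stops

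*Protocol*

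**What the plan says.** The infant regimen follows the mother's allocation. Section 10 (Infant, Daily Vitamin D Supplementation) states "Infants of mothers who receive 6600 IU of vitamin D₃ will receive placebo drops", and Section 1 (Aim 1) states "Those infants of lactating mothers assigned to Group B will receive placebo". Group A infants receive 400 IU/day directly, which Section 1 describes as recommended practice.

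The reason for placebo in Group B is transfer through milk. Hypothesis 2 in Section 1 rests on it, and Section 15, item 4, says of deficient breastfeeding mothers that "there is a need to supplement either the infant directly or the mother herself".

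On feeding after entry:
- Section 5 requires documented full breastfeeding as an inclusion criterion only.
- Section 10 records infant diet, including formula supplementation, at months 1, 2 and 3. No action is attached.
- Section 14 does not list loss of milk among the grounds for withdrawal.
- Section 2 says that preterm infants not fed mother's "own milk (MoM) are given donor breast milk", and that "through pasteurization there is 10-20% less vitamin D".

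The rescue in Section 15, item 4, begins "As an additional safety measure, if at visit 4, any infant in any treatment arm". It gives 400 IU/day if 25(OH)D is below 20 ng/mL.

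**The concern.** Placebo drops are defensible in Group B while the mother's milk carries the vitamin D. If that milk stops, neither of the routes named in Section 15 supplies the infant from the study: the drops are placebo and the mother's dose no longer reaches the child. Group A infants are not exposed to this, because their dose does not depend on milk.

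Followed as written, the Protocol keeps a preterm infant on placebo after its own reason for withholding the recommended dose has gone. It sets no study dose in response until month 3, and then only if the level is already low. Section 15 names the risk of hypovitaminosis D for Group A infants who miss their drops, but not the matching risk for Group B infants who lose mother's milk. This is an infant safety point. A dosing rule of this kind belongs in the protocol, not in a statistical analysis plan.

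**Working it through.** The Protocol states no figure to reproduce. The check is mainly a reading of the rules, with three small calculations for scale.

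**1. When can the drops change?** Section 10 sets visits at about days 3-7 and months 1, 2 and 3, so visit 4 is month 3. Section 4 measures the primary outcomes at month 3, so the rescue comes at the end of the intervention period.

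| Provision | Trigger | Changes the study drops or sets a dose? |
|---|---|---|
| Section 10, Infant item 5: monthly infant 25(OH)D, notice to parents and physician | Deficiency found | No; follow-up is recommended |
| Section 13, B: DSMB notice | Value out of range | No |
| Section 15, item 4: rescue | Below 20 ng/mL at visit 4 | Sets 400 IU/day |
| Section 15, item 4: second rule | Below 10 ng/mL with low calcium, at 3 months or older | No; compliance review, then referral |
| Section 14: withdrawal | Moving, transfer, baseline calcium abnormality | Not triggered by loss of milk |

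No row is triggered by feeding, and none sets a study dose before month 3.

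**2. Is the event foreseeable?** The infant questionnaire asks about formula supplementation, and Section 2 discusses preterm infants not fed mother's own milk. Aim 1 also studies supplementation "as a function of maternal vitamin D status, lactation status, and ethnicity". That phrase is weaker evidence, since Section 15, item 3, mentions non-lactating controls whom Section 5 does not enrol.

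**3. Share of the arm.** Section 6 gives 25 dyads per group. One infant is 1/25 = 4%; five would be 5 × 4% = 20%. The documents give no rate of lactation loss, so the number affected cannot be estimated.

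**4. Wait until feeding status is next recorded**, taking 30-day months. From the initial visit to month 1: 30 − 7 = 23 to 30 − 3 = 27 days. Between later visits: 60 − 30 = 30 and 90 − 60 = 30 days. With a feeding-triggered rule, the longest wait would be about 30 days, and less in the NICU.

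**5. Worst-case intake, as illustration only.** Section 2 says of a deficient mother that "her milk provides limited vitamin D, with roughly 3-4 IU/kg/day provided". Assume donor milk has that content, no fortifier or formula is used, and the infant weighs 1-3 kg (assumed).
- Low: 3 × 0.80 = 2.4 IU/kg/day. High: 4 × 0.90 = 3.6 IU/kg/day.
- Per day: 1 × 2.4 = 2.4 IU up to 3 × 3.6 = 10.8 IU.
- Against 400 IU: 2.4/400 = 0.6% to 10.8/400 = 2.7%.

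Fortifier, formula or vitamin D ordered by a clinician would raise this. The documents do not describe their use in the study.

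**The case against.** The other side has good points.

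- **The regimen is written for lactating dyads.** Section 1 speaks of infants of lactating mothers and Section 5 admits only women who are fully breastfeeding. The Protocol could be read as silent on what follows when lactation ends. That is fair as to intent, but it is not a switching rule: the instruction in Section 10 depends only on the mother's dose.
- **Low vitamin D is monitored, whatever its cause.** This stands. Infant 25(OH)D is measured about monthly, with notice to parents, physician and DSMB, and treating clinicians, who may include study staff, can act. What remains is that nothing happens on loss of milk alone, and the study drops do not change.
- **The intake percentages are extreme.** This also stands. The 3-4 IU/kg/day describes a deficient mother's milk, not donor milk, and formula is the supplement that the questionnaire actually tracks.

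A reader might infer that no rule ever changes the drops. Section 15 does not support that: the visit-4 rescue covers any infant in either arm. A reader might also infer that infants go unmonitored, that many are affected, or that the month-3 comparison is biased. The documents show monthly checks, give no rate of lactation loss, and provide no basis for calculating an effect on the outcome.

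**Conclusion.** The point holds as a narrow safety gap that should be closed. Before the month-3 rescue, no rule changes a Group B infant's study drops when mother's own milk stops, although milk is that infant's only study route of vitamin D. The existing checks are partial safeguards that wait for a low level.

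The size is 4% of the arm per infant, with the number of infants unknown. The conclusion rests on the wording of Sections 1, 5, 10, 13, 14 and 15, and needs no assumption about how much vitamin D the substitute feed contains. The 0.6-2.7% range is a worst case and carries no weight in the conclusion.

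**What to change.** **Section 10, Infant, Daily Vitamin D Supplementation.** Add: when the Breastfeeding Review or Infant Health/Diet questionnaire, or the NICU feeding record, shows that the infant no longer receives mother's own milk, Investigational Drug Services replaces the study drops with 400 IU/day vitamin D drops, in both arms, unless the infant takes at least 1,000 mL/day of vitamin D-fortified formula. Because this is a replacement and not an addition, Group A infants stay at 400 IU, no infant is double-dosed by the study, and the switch does not reveal the arm. The formula threshold comes from the dosing text in Section 3. It will rarely apply: at 1-3 kg it means 1,000/1 = 1,000 down to 1,000/3 ≈ 333 mL/kg/day.

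**Follow-up.** Keep the dyad in its randomised group and record the date and reason of the switch.

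**Section 15, item 4.** Name the Group B risk of hypovitaminosis D when mother's milk is lost.

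**Leave unchanged.** Infants still partly fed mother's milk stay on their assigned drops under the monthly checks, and their rescue stays at visit 4. Section 15 says that steady state takes about 3 months and infant levels rise over 2-3 months, so an earlier rescue for all could move many to the comparator's infant dose before the primary outcome.

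**Cost.** Wording in two sections and a further dispensing of drops. The questionnaires and the vitamin D drops are already in the study; access to the NICU feeding record is assumed. The real price is that each switched Group B infant receives the comparator's infant dose, which dilutes the contrast by 4% of the arm. The total is unknown and may not be small, but these are infants whom the maternal route no longer reaches.
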